## 8.5. Unscheduled Visits

Unscheduled visits are allowed for the following reasons:

- To perform confirmatory laboratory testing for clinically abnormal values; and
- If the PI feels that it is clinically required for safety reasons related to the subject's participation in the study.

Findings during these unscheduled visits must be reported on the eCRF in the Unscheduled Visit section.

### **8.6.** Concomitant Medications

Subjects should not be taking prescription medications or over the counter drugs included in the list of exclusion criteria or on the eligibility assessment questionnaire while participating in this study. If the subject develops a medical condition between the time of plasmapheresis and reinfusion, the medication should be approved by the PI prior to the subject taking the medication. If a medication is taken that is contraindicated to the objectives of the study, the infusion will either be deferred or the subject will be taken off study.

The AABB Medication Deferral List includes:

- Proscar© (finasteride);
- Avodart©, Jalyn (dutasteride);
- Propecia© (finasteride);
- Accutane© (Amnesteem, Claravis, Sotret, isotretinoin);
- Soriatane© (acitretin);
- Tegison© (etretinate);
- Growth hormone from human pituitary glands;
- Insulin from cows (bovine, or beef insulin);
- Hepatitis B immune globulin;
- Plavix (clopidogrel) and Ticlid (ticlopidine);
- Feldene; and
- Experimental medication or unlicensed (experimental) vaccine.

# 8.7. Procedures for Monitoring Subject Compliance

A record of each study plasma infusion will be documented in the clinical database via relevant eCRFs and additional source documentation. Only the individual product unit identifier will be stored in the clinical database. The clinical database will document that the infusion occurred. Additionally, for unit identifiers documented in the clinical database, final disposition will be reconciled by linking to a separate Plasma Unit Tracking Form that will be maintained by 5th floor HBC FDP research staff and VSI.

#### 9. PHARMACOKINETIC ASSESSMENTS

No pharmacokinetic assessments will be done in this study.

#### 10. SAFETY ASSESSMENT

Safety monitoring throughout the study will identify safety issues and concerns. The process of continual review of the data and the imperative to appropriately and promptly address identified safety concerns is a shared effort of the PI and clinic staff, the designated clinical and research monitors, USAMRMC USAMMDA ORA, and the PVG MD for the protocol. A DSMB will be convened for this protocol. The roles and responsibilities of the monitors and DSMB are outlined below.

Clinical Site: Consists of the PI, RM, Clinical Research Coordinator, and other research staff. The clinical site is responsible for ensuring the safety of study subjects by managing, collecting, and recording AEs/SAEs, and reporting SAEs appropriately according to the requirements of the protocol and their local IRB. The PI will promptly forward all SAEs to the IRB and HRPO.

Research Monitor: The Department of Defense research monitor is responsible for overseeing the safety of the research and reporting observations/findings to the IRB or a designated institutional official. The research monitor will review all unanticipated problems involving risks to subjects or others associated with the protocol and provide independent reports of the events to the IRB. The research monitor may discuss the research protocol with the investigators; shall have authority to stop a research protocol in progress, remove individual human subjects from a research protocol, and take whatever steps are necessary to protect the safety and well-being of human subjects until the IRB can assess the monitor's report; and shall have the responsibility to promptly report their observations and findings to the IRB or other designated official and the HRPO.

In addition to the responsibilities above, the research monitor is required to review and provide unbiased written reports for all SAEs and subject deaths to the USAMMDDA PSSB (Safety Office) within 24 hours of becoming aware of the event. The report provided must include at a minimum, a brief summary of the research monitor's review of the event and event outcome, relationship of the event to the investigational product, and whether or not the research monitor concurs with the details of the study investigator's report.

Clinical Monitor: The designated clinical monitor for the trial is to:

- 1. Conduct initial, periodic, and termination clinical site visits;
- 2. Check that the clinical site is adhering to the protocol in its conduct of the study and to information presented in the informed consent documents, SOPs, and applicable regulations;
- 3. Oversee study file and regulatory documents, and cross check source documents and eCRFs; and
- 4. Observe study procedures.

## Pharmacovigilance Physician:

The USAMMDA Safety PVG MD, as delegated by the sponsor, evaluates all safety cases and provides a final determination on relatedness to the product and whether expedited reporting is warranted per current FDA regulation and guidance. In coordination with USAMRMC USAMMDA ORA, each SAE report is reviewed for medical consistency, accuracy, and completeness and each event followed until it is satisfactorily resolved. In addition, the PVG MD will serve as an arbiter in cases where the PI and RM's review of these data results in discordant determinations.

The PVG MD is responsible for the review of SAE data and reports. In reviewing SAEs, the PVG MD will:

- 1. Review SAE reports to ensure the content is medically consistent, accurate, and complete;
- 2. Follow each SAE until it is satisfactorily resolved; and
- 3. Perform an assessment of the reporting status to the FDA/DSMB.

**Data and Safety Monitoring Board:** An independent DSMB will be convened to review clinical trial safety data and provide recommendations to the USAMMDA ORA PSSB. The PSSB will deliver the DSMB recommendations to the Sponsor's Representative for final decision. The USAMRMC USAMMDA ORA will communicate the final decision to the PI, who will notify the IRB. USAMRMC USAMMDA ORA will communicate the final decision to the FDA, as appropriate. A further description of the DSMB roles and responsibilities, functions, and reporting requirements is included in the DSMB charter.

# 10.1. Specification of Safety Endpoints

The investigator will review subjects' medical records and administer a focused review of systems and a physical examination to all subjects to determine the presence of symptoms or signs of coagulation abnormalities.

Primary safety endpoints will include those related to vital signs, clinical laboratory parameters (chemistry, hematology, urine analysis, and coagulation), and AEs.

## 10.1.1. Vital Signs

Vital signs to be measured include blood pressure, heart rate, respiration rate, and oral temperature. Vital sign measurements are collected at every on-site visit as part of the physical examination process. During and after the infusion process, vital sign measurements are used to observe for evidence of acute transfusion reactions (eg, bradycardia, tachycardia, cardiac dysrhythmia, hypertension, hypotension, fever, etc.) and are collected every 15 minutes ( $\pm$  5 minutes) during the infusion, every 30 minutes ( $\pm$  5 minutes) between 0 and 4 hours postinfusion, and then every 4 hours ( $\pm$  40 minutes) until the subject is released from the clinic. Temperature will be standardly evaluated following HBC's SOP, Welch Allyn Spot Vital Sign Procedure (# WB-032-SOP).

## 10.1.2. Laboratory Assessments

Laboratory assessments should be performed whenever possible in a College of American Pathologists (CAP)/Clinical Laboratory Improvement Act certified environment or at least, following SOP-driven, QC-reviewed procedures.

The total amounts of blood drawn from a study subject who completes all study procedures are shown in Table 7 and Table 9.

## 10.1.2.1. Hematology and Clinical Chemistry

Table 11 summarizes the hematology and clinical chemistry markers that subjects will be tested for at the specified time points in the study.

**Table 11:** Hematology and Clinical Chemistry Tests

	Pre-Infusion				Po	st-Infusior	1		
HEMATOLOGY	Screening	Collection Day	Infusion Day	0.5 Hours	4 Hours	24 Hours	7 Days	28 Days	Early Withdrawal
CBC (Hematocrit, Hemoglobin, Platelet Count, RBC Count, WBC Count)	X		X	X	X	X	X	X	X
DAT (IgG and C3)	X		X			X		X	X
Hematocrit		X							
Cross-match RBC			X						
Reverse Type FDP/FFP			X						
Blood Type (ABO and Rh)	X		X						
Red-Cell Antibody Screen	X								
Syphilis Screen	X								
Screening Test for HTLV Antibody	X								
Nucleic Acid Tests for HIV-1/2, HBV, HCV, and West Nile Virus	X								
CLINICAL CHEMISTRY									
ALP	X		X	X	X	X	X		X
ALT	X		X	X	X	X	X		X
AST	X		X	X	X	X	X		X
Ionized Calcium; Total Magnesium			X	X					
Electrolytes (Calcium, Chloride, Potassium, Sodium, Lactate, Bicarbonate)	X		X	X	X	X	X		X
рН			X	X					
Glucose	X		X	X	X	X	X		X
Total Bilirubin	X		X	X	X	X	X		X
Total Protein	X		X	X	X	X	X		X
BUN	X		X	X	X	X	X		X
Creatinine	X		X	X	X	X	X		X
SPEP (All subjects undergoing plasmapheresis)		X							
Total Protein (All subjects undergoing multiple plasmapheresis sessions)		X							

## **10.1.2.2.** Urinalysis

A clean-catch urine sample will be collected from all subjects at the screening visit to confirm study eligibility prior to enrollment. Additional urine samples will be collected from enrolled subjects on the day(s) they are infused and at the 24-hour post-infusion follow-up visit(s). The urinalysis will include:

- Visual exam urine sample will be inspected for color and clarity; and
- Chemical exam reagent test strips will be used to determine specific gravity, pH, as well as detect the presence of protein, glucose, ketones, blood, leukocyte esterase, nitrite, bilirubin, and urobilinogen.

## 10.1.2.3. Coagulation Markers

Table 12 summarizes the coagulation markers subjects will be tested for at the specified time points in the study.

**Table 12:** Coagulation Tests

		Pre-Infusion		Pos	t-Infusion		Early
Coagulation Tests	Screening	Infusion Day	0.5 Hours	4 Hours	24 Hours	28 Days	withdrawal
ALL SUBJECTS:	'					1	 
PT/INR	X	X	X	X	X	X	X
aPTT	X	X	X	X	X	X	X
D-Dimer	X	X	X	X	X		X
COHORT 3 SUBJECTS	ONLY:						
Factor I		X	X	X			X
Factor II		X	X	X			X
Factor V		X	X	X			X
Factor VII		X	X	X			X
Factor VIII		X	X	X			X
Factor IX		X	X	X			X
Factor X		X	X	X			X
Factor XI		X	X	X			X
von Willebrand Factor activity		X	X	X			X
Protein C activity		X	X	X			X
Protein S activity		X	X	X			X

## **10.1.2.4. Drug Screen**

A urine drug screening will be performed for Cannabinoids, cocaine, amphetamines, opiates and PCP (NIDA-5) at the screening visit only. Potential subjects with a positive urine drug screen will be ineligible for enrollment.

### 10.1.2.5. Pregnancy Screen

An FDA-cleared qualitative urine pregnancy test that evaluates human beta-chorionic gonadotropin will be used to test all females (at screening, pre-infusion, and early withdrawal ONLY).

# 10.2. Investigational New Drug Safety Reporting

The following terms, as defined by 21 CFR 312.32, apply to this protocol.

### 10.2.1. Adverse Event or Suspected Adverse Reaction

An AE is defined as any untoward medical occurrence associated with the use of a drug/biologic in humans, whether or not it is considered to be related to the drug/biologic.

A suspected AR is any AE for which there is a reasonable possibility that the drug/biologic caused the AE. For the purposes of IND safety reporting, a "reasonable possibility" means there is evidence to suggest a causal relationship between the drug/biologic and the AE. Suspected AR implies a lesser degree of certainty about causality than AR, which means any AE caused by a drug/biologic.

An AE or suspected AR is considered "life-threatening" if, in the view of either the investigator or sponsor, its occurrence places the patient or subject at immediate risk of death. It does not include an AE or suspected AR that, had it occurred in a more severe form, might have caused death.

## 10.2.2. Serious Adverse Event or Serious Suspected Adverse Reaction

An AE is considered "serious" if, in the view of either the PI or sponsor, it results in any of the following outcomes:

- Death;
- A life-threatening AE;
- Inpatient hospitalization or prolongation of existing hospitalization;
- Persistent or significant incapacity or substantial disruption of the ability to conduct normal life functions; or
- Congenital anomaly/birth defect.

Important medical events that may not result in death, be life-threatening, or require hospitalization may be considered serious when, based upon appropriate medical judgment, they may jeopardize the patient or subject and may require medical or surgical intervention to prevent 1 of the outcomes listed in this definition. Examples of such medical events include allergic bronchospasm requiring intensive treatment in an emergency room or at home, blood dyscrasias

or convulsions that do not result in inpatient hospitalization, or the development of drug dependency or drug abuse.

## 10.2.3. Unexpected Adverse Event or Unexpected Suspected Adverse Reaction

An unexpected adverse event (UAE) or unexpected suspected AR is an AE that is not:

- Listed in the Investigator's Brochure (IB);
- Listed at the specificity or severity that has been observed; or
- Consistent with the risk information described elsewhere in the current application.

For example, if the IB referred only to elevated hepatic enzymes or hepatitis as expected AEs, under this definition, hepatic necrosis would be a UAE by virtue of the greater clinical severity. Similarly, if the IB only listed cerebral vascular accidents as an expected AE, the occurrence of cerebral thromboembolism and cerebral vasculitis would be a UAE by virtue of greater specificity. "Unexpected," as used in this definition, also refers to AEs or suspected ARs that are mentioned in the IB as occurring with a class of drugs/biologics or as anticipated from the pharmacological properties of the drug/biologic, but are not specifically mentioned as occurring with the particular drug/biologic under investigation.

## 10.2.4. Expected Adverse Events

An expected AE is a predetermined event, identified in the IB. The following expected AEs for this study include:

- Pain, bleeding, bruising, scarring, and local infection associated with fingerstick blood sampling procedures;
- Pain/soreness, bruising, discoloration, swelling, blood clot or bleeding, nerve damage, arterial puncture, local infection, dizziness, light-headedness, syncope, fatigue, iron deficiency with or without anemia associated with venipuncture;
- Blood loss from the inability to return RBCs during automated plasmapheresis procedures;
- Tingling of lips or fingers or muscle cramping, spasms, seizures, tetany, cardiac arrhythmia due to the citrate anticoagulant used in an automated plasmapheresis procedure;
- Allergic reactions such as flushing, itching, hives, abdominal cramps, difficulty breathing, chest pain, or bronchospasm, which may vary in severity from mild to life-threatening associated with both plasmapheresis donation and plasma infusion;
- Nausea, unpleasant taste, vomiting, light-headedness, fainting, malaise, or seizures associated with both plasmapheresis donation and plasma infusion;
- Non-immunologic complications such as the transmission of infectious agents, bacterial sepsis, transfusion-associated circulatory overload, hypothermia-cardiac arrhythmias;
- Metabolic complications such as citrate toxicity-hypocalcemia, acidosis, alkalosis, hyperor-hypokalemia, and coagulopathies; and

• Transfusion reactions.

## 10.2.5. Unanticipated Problems Involving Risks to Subjects or Others

Federal regulations require that unanticipated problems involving risks to subjects or others be promptly reported to the IRB. These events encompass a broader category of events than SAEs, and may include issues such as problems with loss of control of subject data or the investigational product; adverse psychological reactions; or breach of confidentiality. Risks to others (eg, program personnel) must also be reported.

Unanticipated problems involving risks to subjects or others are any incident, experience, or outcome that meets all of the following criteria:

- Unexpected (in terms of nature, severity, or frequency) given (a) the procedures that are described in the protocol, IB, or informed consent document; and (b) the characteristics of the subject population;
- Related or possibly related to a subject's participation in the study; and
- Suggests that the study places subjects or others at a greater risk of harm than was previously known or recognized.

The clinical site's IRB and the USAMRMC's HRPO will evaluate the PI's and RM's reports to determine whether or not a given incident, experience, or outcome constitutes an unanticipated problem involving risk to subjects or others, and will ensure reporting of the unanticipated problems involving risk to subjects or others to the appropriate regulatory offices, as applicable.

# 10.3. Relationship to Investigational Product

The site PI must assign a relationship of each AE to the receipt of the investigational product. The PI will use clinical judgment in conjunction with the assessment of a plausible biologic mechanism, a temporal relationship between the onset of the event in relation to receipt of the investigational product, and identification of possible alternate etiologies including underlying disease, concurrent illness, or concomitant medications. The following guidelines should be used to assess the relationship of an AE to study product administration and **ONLY A PHYSICIAN CAN MAKE THIS DETERMINATION:** 

**Not related:** There is no reasonable causal relationship between the investigational product administered and the SAE. Applies to those events for which an alternate etiology exists.

**Unlikely:** Likely unrelated to the investigational product. Likely to be related to factors other than investigational product, but cannot be ruled out with certainty.

**Possible:** An association between the event and the administration of investigational product cannot be ruled out. There is a reasonable temporal association, but there may also be an alternative etiology such as the subject's clinical status or underlying factors including other therapy.

**Probable:** There is a high degree of certainty that a relationship to the investigational product exists. There is a reasonable temporal association, and the event cannot be explained by known characteristics of the subject's clinical state or factors including other therapy.

**Definite:** An association exists between the receipt of an investigational product and the event. An association to other factors has been ruled out.

# **10.4.** Severity Assessment

All AEs will be assessed for severity by the PI. Inherent in this assessment is the medical and clinical consideration of all information surrounding the event including any medical intervention required. The PI will use the CDC National Healthcare Safety Network Hemovigilance Module criteria (Appendix I) to define transfusion-related AEs.. The NCI Common Terminology Criteria for toxicity grade will be used to assign the severity for all AEs (transfusion and non-transfusion related) (HHS-2010). The criteria below may be used for any symptom not included in the grading scale. Any Grade 4 (life-threatening) or Grade 5 (fatal) AE must be reported as an SAE.

The eCRF for AEs will reflect only the highest severity for continuous days an event occurred.

Mild	Grade 1	Does not interfere with routine activities Minimal level of discomfort
Moderate	Grade 2	Interferes with routine activities Moderate level of discomfort
Severe	Grade 3	Unable to perform routine activities Significant level of discomfort
Life-threatening	Grade 4	Potentially life threatening or life-threatening and requires hospitalization, emergency room visit, or urgent intervention
Fatal	Grade 5	Death

The terms "serious" and "severe" are not synonymous. The term "severe" describes the intensity of a specific event (eg, mild, moderate, or severe headache), whereas the event itself may not meet the seriousness criteria.

If a subject is evaluated in an emergency room for non-life-threatening illness or symptoms (i.e., visits emergency department on weekend for mild problems because the physician's office is closed), the information from that visit will be reviewed and severity of the AE will be assessed according to the subject's clinical signs and symptoms.

As defined by the ICH guideline for GCP, the term "severe" is often used to describe intensity (severity) of a specific event (as in mild, moderate, or severe myocardial infarction); the event itself however, may be of relatively minor medical significance (such as severe headache). This is **not** the same as "serious," which is based on subject/event **outcome** or **action** criteria usually associated with events that pose a threat to a subject's life or functioning. Seriousness (not severity) serves as a guide for defining regulatory reporting obligations.

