## 10.5.1. Methods and Timing for Assessing, Recording, and Analyzing Adverse Events

All AEs will be assessed at all study visits, documented in the source records, and recorded on the eCRFs using accepted medical terms and/or the diagnoses that accurately characterize the event. When a diagnosis is known, the AE term recorded on the eCRF will be the diagnosis rather than a constellation of symptoms. The PI will assess and record for all AEs/SAEs: a description of the event (if the event consists of a cluster of signs and symptoms, a diagnosis should be recorded rather than each sign and symptom); onset date and time, and stop date and time; intensity (recorded as mild, moderate or severe); seriousness; causality (relationship to study drug); outcome (eg, resolved, resolved with sequelae, not resolved, fatal, or unknown if applicable); action taken with the study agent (eg, no action, study agent discontinued and other action taken).

When an event is not resolved by study closure, it will be documented on the AE eCRF as ""not recovered/not resolved".

AEs will be assessed using an open-ended question such as: "How have you been feeling since we last spoke?" If an AE that requires medical attention is reported to a nurse, it should be reported to a study physician immediately. The PI or study physician will assess subjects for any medical side effects, through a focused review of systems and physical exam. Specifically, they will be looking for evidence of coagulation disturbances. Subjects with suspected positive findings will be referred to their treating physicians for clinically indicated and appropriate evaluation and management. Acute plasma infusion reactions will also be specifically documented as follows:

- Fever (by oral or axillary temperature);
- Allergic reactions (i.e., skin rash; urticarial; pruritus; generalized flushing; localized angioedema; edema of the lips, tongue, or uvula; erythema of the periorbital area; conjunctival edema by physical exam);
- Bronchospasm (by symptoms);
- Chills (by subject report after specific query by clinical staff);
- Tachycardia, bradycardia, other dysrhythmias, dyspnea, hypertension, hypotension (by vital sign measurements heart rate, blood pressure, and respiration rate);
- Hemolysis or acute hemolytic transfusion reactions resulting in circulatory/cardiovascular dysfunction (by clinical laboratory result); and
- Infection (by physical exam or clinical laboratory results).

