# 11.1.1. Endpoints for Primary Study Objective Analyses

The primary endpoints for the study to be assessed are specifically:

- TEAEs;
- SAEs:

- Suspected, unexpected, serious adverse reactions (SUSARs); and
- Deaths.

Safety endpoints for subjects' that will be assessed just prior to infusion and again after infusion include evaluations presented in sections 8.2 and 8.3.

Descriptive statistics will be used to analyze the primary safety endpoints. Tables produced to exhibit the primary safety endpoint data will be presented by the specific type of plasma product infused. In Cohorts 1 and 2, this data will be presented by FDP product type, FDP-ACD and FDP-CPD; in Cohort 3 by experimental product and control product, FDP-ACD and FFP. The primary safety data reported to the DSMB for Cohort 3 will be masked. Unblinding during the study will only occur in accordance with section 6.6.3.

In general, AEs that occur in Cohort 3 subjects within 14 days after infusion will be attributed to the most recently infused product. However, there may be exceptions to use of this temporal attribution rule to all transfusion-related AEs given the possibility that those AEs that occur after infusion with the second product may potentially be related to infusion with the first infusion product (e.g., an immunogenic response).

The safety endpoints measured prior to the infusion will serve as the "baseline" to which all subsequent measurements will be compared.

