4.5.3.1 Primary Safety Endpoints

The primary safety endpoints to be assessed are AEs, specifically:

- TEAEs;
- SAEs;
- SUSARs; and
- Deaths.

Descriptive statistics will be used to analyze the primary safety endpoints. Tables produced to exhibit the primary safety endpoint data will be presented by the specific type of plasma product infused. In Cohorts 1 and 2, this data will be presented by FDP product type, FDP-ACD and FDP-CPD; in Cohort 3 by experimental product and control product, FDP and FFP. The primary safety data reported to the DSMB for Cohort 3 will be masked. Unblinding during the study will only occur in accordance with Section 3.3.2 following Westat's SOP DA-504 Development of a Plan for Randomization, Masking, and Unmasking.

In general, AEs that occur in Cohort 3 subjects within 14 days after infusion will be attributed to the most recently infused product. However, there may be exceptions to use of this temporal attribution rule to all transfusion-related AEs given the possibility that those AEs that occur after infusion with the second product may potentially be related to infusion with the first infusion product (e.g., an immunogenic response).

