Subject ID	Sex/Age	Infusion Number [1]	Visit	Collection Date/Time	Vital Sign Test	Result	Unit
XXXXXX	X/XX	X	X	DDMMYY:TT	XXXXX	XXXXX	XXXXX
		X	X	DDMMYY:TT	XXXXX	XXXXX	XXXXX
		X	X	DDMMYY:TT	XXXXX	XXXXX	XXXXX
		X	X	DDMMYY:TT	XXXXX	XXXXX	XXXXX
XXXXXX	X/XX	X	X	DDMMYY:TT	XXXXX	XXXXX	XXXXX
		X	X	DDMMYY:TT	XXXXX	XXXXX	XXXXX
		X	X	DDMMYY:TT	XXXXX	XXXXX	XXXXX
		X	X	DDMMYY:TT	XXXXX	XXXXX	XXXXX

[1] Infusion Number: 1=Infusion #1; 2=Infusion #2.

Program Path:
Data source: ADVS

Data extract date:

Listing 13. Treatment-Emergent Adverse Events

Arm: XXXXXX

Subject ID	Sex/Age	Date of Enrollment	Randomization Date	Adverse Event Start Date	Body System or Organ Class	Preferred Term	Ongoing	Toxicity Grade [1]	Serious	Related to Study Drug [2]	Action Taken [3]	Outco [4]	
											Related to Study Drug [2]	Action Taken [3]	Outco [4]
XXXXXX	X/XX	DDMMYYYY	DDMMYYYY	DDMMYYYY	XXXXXXXXXXXX	XXXXXXXXXXXX	X	X	X	X	X	X	X
XXXXXX	X/XX	DDMMYYYY	DDMMYYYY	DDMMYYYY	XXXXXXXXXXXX	XXXXXXXXXXXX	X	X	X	X	X	X	X
XXXXXX	X/XX	DDMMYYYY	DDMMYYYY	DDMMYYYY	XXXXXXXXXXXX	XXXXXXXXXXXX	X	X	X	X	X	X	X
XXXXXX	X/XX	DDMMYYYY	DDMMYYYY	DDMMYYYY	XXXXXXXXXXXX	XXXXXXXXXXXX	X	X	X	X	X	X	X
XXXXXX	X/XX	DDMMYYYY	DDMMYYYY	DDMMYYYY	XXXXXXXXXXXX	XXXXXXXXXXXX	X	X	X	X	X	X	X

[1] Grade 1=Mild; 2=Moderate; 3=Severe; 4=Life-Threatening; 5=Fatal.

[2] Related to Study Drug: 1=Not Related; 2=Unlikely; 3=Possible; 4=Probable; 5=Definite.

[3] Action Taken: 1=Dose Increased; 2=Dose Not Changed; 3=Dose Reduced; 4=Drug Interrupted; 5=Drug Withdrawn; 6=Not Applicable; 7=Unknown.

[4] Outcome: 1=Recovered/Resolved; 2=Recovered/Resolved with Sequelae; 3=Recovering/Resolving; 4=Not Recovered/Not Resolved; 5=Fatal; 6=Unknown.

Listing 14. Listing of Unique Adverse Events

Arm: XXXXXXX

Body System or Organ Class	Preferred Term	Reported Term for the Adverse Event
XXXXXXXXXXXXXX	XXXXXXXXXXXX	XXXXXXXXXXXX

Note: Terms are sorted by reported term.

Program Path:
Data source: ADAE

Data extract date:

Listing 15. Treatment-Emergent Adverse Events at Least Probably Related to Study Drug

Arm: XXXXXXX

Subject ID	Sex/Age	Date of Enrollment	Randomization Date	Adverse Event Start Date	Body System or Organ Class	Preferred Term	Ongoing	Toxicity Grade [1]	Serious	Related to Study Drug [2]	Action Taken [3]	Outc [4]
XXXXXX	X/XX	DDMMYY	DDMMYY	DDMMYY	XXXXXXXXXXXX	XXXXXXXXXX	X	X	X	X	X	X
XXXXXX	X/XX	DDMMYY	DDMMYY	DDMMYY	XXXXXXXXXXXX	XXXXXXXXXX	X	X	X	X	X	X
XXXXXX	X/XX	DDMMYY	DDMMYY	DDMMYY	XXXXXXXXXXXX	XXXXXXXXXX	X	X	X	X	X	X

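### In Cohort 3, an adverse event that worsens across infusion 2 can carry its later grade against the first product, and exceptions to the attribution rule need not be settled before unblinding

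*Protocol*

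**What the plan says.** **Recording.** The grading rule in Protocol 10.4 is that "The eCRF for AEs will reflect only the highest severity for continuous days an event occurred", with no separate provision for the crossover cohort. For each AE, Protocol 10.5.1 asks for "onset date and time, and stop date and time", an intensity, and "seriousness; causality (relationship to study drug); outcome". Protocol 10.3 adds that "The site PI must assign a relationship of each AE to the receipt of the investigational product". Neither a date of grade change nor a suspected infusion is among the items listed. SAP Listing 13 shows a start date, an ongoing flag, one toxicity grade and one five-level relatedness code. It has no infusion number, although the vital-sign Listings 10 to 12 do.

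**Attribution.** Protocol 11.1.1 and SAP 4.5.3.1 share one rule: in general, "AEs that occur in Cohort 3 subjects within 14 days after infusion will be attributed to the most recently infused product". Both then say that "there may be exceptions to use of this temporal attribution rule to all transfusion-related AEs", because an event after the second infusion may stem from the first. Neither gives criteria, a decision-maker or a time.

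**Worsening.** The definition of a treatment-emergent AE (TEAE) in Protocol 11.1.3 and SAP 4.5.3 covers new onset and is silent on worsening. Protocol 10.5.2 treats progression of a serious AE (SAE) as follow-up to the original report.

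**Display.** The text of Protocol 11.1.1 and SAP 4.5.3.1 promises Cohort 3 primary safety data by product. The AE shells in SAP section 5 use masked columns A and B, relabelled at final analysis with the two sequences.

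**The concern.** One grade per continuous event and one relatedness rating suit Cohorts 1 and 2, where each subject has a single infusion. In Cohort 3 each subject has two infusions of different products, and an event can run across the second. The highest grade over the whole run may then belong to a different product from the one in force at onset, and the listed data would not show it. The exception raises a related issue. It changes which product an event is counted against, yet the plan does not fix it at a point when the decision-maker is certain to be blind.

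At stake is the FDP versus FFP safety comparison (secondary objective 1). The Data and Safety Monitoring Board's recommendation on the next FDP trial also follows its review of Cohort 3 data.

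**Working it through.** **1. The plan's own precision figure.** Protocol Table 16 and SAP Table 3 give Clopper-Pearson limits. For n = 24 and incidence 10%, x = 2.4. The lower limit is the 0.025 quantile of Beta(x, n−x+1) and the upper is the 0.975 quantile of Beta(x+1, n−x). This gives 1.6% to 29.2%, width 27.6, as stated, and all nine cells reproduce. That figure covers all 24 subjects, whereas the product comparison rests on 8. By the same formula, 0/8 gives 0 to 36.9% and 1/8 gives 0.3 to 52.7%.

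**2. One event followed through the rules.** Suppose an AE begins at Grade 1 after infusion 1, does not resolve, and reaches Grade 3 after infusion 2.
- Protocol 10.4: the days are continuous, so one grade is kept, Grade 3.
- Protocol 10.5.1: the onset recorded is in period 1, and no date of worsening is listed.
- Protocol 11.1.1 and SAP 4.5.3.1, applied by onset: the event belongs to the first product.
- TEAE definition: the event was already present at infusion 2, so the worsening is not clearly a new TEAE for the second product.

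This subject's contribution to incidence, with 8 subjects per product and assuming no other such event in the subject:

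| Count | First product | Second product | First minus second |
|---|---|---|---|
| Grade 3 or above, as planned | 1/8 | 0/8 | +12.5 points |
| Grade 3 or above, worsening recorded separately | 0/8 | 1/8 | −12.5 points |
| Any grade, as planned | 1/8 | 0/8 | +12.5 points |
| Any grade, worsening recorded separately | 1/8 | 1/8 | 0 |

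The change is (1/8 − 0/8) − (0/8 − 1/8) = 0.25 at Grade 3 or above, and 0.125 for any grade. Moving a whole event under the exception also gives 0.25.

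**3. How often.** The documents give no rate, so these are assumptions.
- If each subject has probability q of an affected event, the chance of at least one among 8 is 1 − (1 − q)^8. For q = 2%, 5%, 10% and 20% this is 15%, 34%, 57% and 83%.
- The share of period-1 events still ongoing at infusion 2, 14 days later, with uniform onset and exponential duration of mean d days, is (d/14)(1 − e^(−14/d)). For d = 1, 2, 3 and 7 this is 7%, 14%, 21% and 43%.
- If onset is on Day 1, the share is e^(−14/d): under 1% at d = 3 and 14% at d = 7.

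Only the ongoing events that then worsen are misgraded. No worsening fraction is available.

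**4. Timing of the exception.** Protocol 6.6.2 blinds the investigator, the research monitor and the pharmacovigilance physician to sequence. Protocol 6.6.3 puts planned unblinding after database lock. Choosing between infusion 1 and infusion 2 needs no knowledge of product, so the choice can be made blind. No section requires it to be made or documented before lock.

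**The case against.** The strongest reply has five parts.

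- **Unblinding.** A reader might infer that the plan reassigns events after the code is broken. No section says so. The investigator is blinded and lock comes before unblinding. What stands is only that the timing is unspecified.
- **Direction and reach.** A reader might see the exception as one-sided, or as open to every event after infusion 2. It is limited to transfusion-related AEs and runs in the only direction causality allows, since infusion 2 cannot cause an event confined to the time before it. Banning it would count a delayed immune response to the first product, the documents' own example, against the second. This objection stands, and the exception should be kept.
- **Lost information.** It would be too strong to say that the worsening leaves no trace. AEs are documented in source records at every visit. The Appendix I worksheet for transfusion-related AEs records the reaction date and time and the transfusion end time. The SAE form has a table of doses and dates. Onset period can be derived from Listing 13 and the infusion dates in Listing 8. But Appendix I states that it is not a case report form, the SAE form covers SAEs only, and neither puts the date of grade change into the listed AE data.
- **Tables.** A reader might infer that planned tables already credit events to the wrong product. As drawn, the Cohort 3 AE shells count by sequence, so they credit no event to either product. This does not rescue the plan: the promised by-product tables need a product for every AE, and the difficulty arises once they are built.
- **Form design.** The AE form is not in the documents. That a continuous event forms one record is the natural reading of Protocol 10.4 and 10.5.1, not a stated fact.

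**Conclusion.** The point holds in a conditional form. As written, an unbroken Cohort 3 AE that worsens after infusion 2 would carry its second-period grade against the first product, if attribution follows onset and the form keeps one record per continuous event. Separately, the exception for transfusion-related AEs has no named decision-maker or deadline, so nothing requires it to be settled before unblinding. The documents do not show that attribution is changed after unblinding.

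The circumstances are probably rare in 8 healthy volunteers: an event must span infusion 2 and worsen, or be judged due to the earlier infusion. One such case would still move the FDP-minus-FFP difference by 25 points for the affected count. The study is descriptive, so no test, alpha or sample size is affected. The change is worth making because grade by period and a blinded view of the responsible infusion are hard to rebuild reliably afterwards.

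**What to change.** 1. **Grading.** For Cohort 3, amend Protocol 10.4 so that a grade increase after the start of infusion 2 in an ongoing AE is entered as a new record with its own onset and grade, or record the grade separately for each period. Count the worsening as treatment-emergent for the second product. Align the TEAE definition (Protocol 11.1.3, SAP 4.5.3) and the SAE follow-up wording (Protocol 10.5.2), so that the clinical and safety databases can still be reconciled.
2. **Exception.** Keep it in Protocol 11.1.1 and SAP 4.5.3.1. Require the blinded investigator to decide it by infusion number, in one added AE form field, and to document it before database lock. Show the strict temporal attribution alongside as a sensitivity count.
3. **Display.** Reconcile the Cohort 3 AE shells in SAP section 5, now labelled by sequence, with the by-product presentation in the text.

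The cost is one form field, short wording changes in both documents and revised shells. A worsening event will appear as two records, so event counts rise slightly. Within each product a subject is still counted at most once. Treatment, sample size and blinding are unchanged.
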